2.1 Schedule of Activities: Screening Through Treatment Phase

| Trial Period | Screening | | | | | Reminder Contacts (Monthly) | Notes |
|--------------------------------------------------|-------------------|----------------------|------------------------|------------------------|----------------------------|-----------------------------|--------------------------------------------------------------------------------------------------------------------------------------------------------|
| Visit Number/Title | Visit 1 Screening | Visit 2 Day 1 Vacc 1 | Visit 3 Month 2 Vacc 2 | Visit 4 Month 6 Vacc 3 | Visit 5 Month 7 | | |
| Scheduled Day | -21 to -1 | 1 | 61 | 183 | 213 | | |
| Scheduling Window | -21 to -1 | Day 1 | ± 21 days | ±28 days | 21 to 49 days after Vacc 3 | | |
| Informed consent | X | | | | | | |
| Informed consent for future biomedical research | X | | | | | | |
| Check inclusion/exclusion criteria | X | X | | | | | |
| Medical history | X | | | | | | |
| Prior/concomitant medication review | X | X | X | X | X | | |
| Full physical examination | | X | | | | | Includes height, weight, vital signs (temperature, heart rate, respiratory rate, and blood pressure), and other assessments specified in Section 9.5.1 |
| Screening for CMV serostatus by IgG | X | | | | | | |
| Serum pregnancy test (β-HCG) | X | | | | | | |
| Participant identification card | X | | | | | | Card provided after informed consent. Site to add randomization number at Visit 2 |
| Treatment randomization | | X | | | | | |
| Urine and saliva sample self-collection training | | X | | | | | Will be performed prior to vaccination |
| Directed physical examination | | | X | X | X | | Includes vital signs (temperature, heart rate, respiratory rate, and blood pressure), and limited assessments specified in Section 9.5.1 |
| Urine pregnancy test | | X | X | X | X | | Will be performed prior to vaccination |

| Trial Period | Screening | | | | | Reminder Contacts (Monthly) | Notes |
|----------------------------------------------------------------------------------------------------------------------------------------------|--------------------------|-----------------------------|-------------------------------|-------------------------------|----------------------------|------------------------------------|-------------------------------------------------------------------|
| Visit Number/Title | Visit 1 Screening | Visit 2 Day 1 Vacc 1 | Visit 3 Month 2 Vacc 2 | Visit 4 Month 6 Vacc 3 | Visit 5 Month 7 | | |
| Scheduled Day | -21 to -1 | 1 | 61 | 183 | 213 | | |
| Scheduling Window | -21 to -1 | Day 1 | ± 21 days | ±28 days | 21 to 49 days after Vacc 3 | | |
| Participants NOT included in the Detailed Immunogenicity sub-study: Serum for NABs and IgG ELISA antibodies | | X | | | X | | Baseline sample to be collected prior to vaccination |
| Detailed Immunogenicity sub-study participants only: Blood for CMV IFN- γ ELISPOT (PBMCs) and serum for NABs and IgG ELISA antibodies | | X | | X | X | | Baseline and Month 6 samples to be collected prior to vaccination |
| Blood (DNA) for future biomedical research | | X | | | | | Will be performed prior to vaccination |
| V160/Placebo administration | | X | X | X | | | |
| 30-minute postdose safety observation | | X | X | X | | | |
| Distribution of eVRC device | | X | | | | | |
| Check postdose 1 exclusion criteria (and any contraindication to vaccination) | | | X | X | | | Will be performed prior to vaccination |

| Trial Period | Screening | | | | | Reminder Contacts (Monthly) | Notes |
|------------------------------------------------------------------------|-------------------|----------------------|------------------------|------------------------|----------------------------|-----------------------------|----------------------------------------------------------------------------------------------------------------------------------------------------------------------------------------------------------------------------------------------------------------------------------------------------------------------------------------------------------------------------------------------------------------------------------------------------------------------------------------------------------------------------------------------------------------------------------------------------------------------------------------------------|
| Visit Number/Title | Visit 1 Screening | Visit 2 Day 1 Vacc 1 | Visit 3 Month 2 Vacc 2 | Visit 4 Month 6 Vacc 3 | Visit 5 Month 7 | | |
| Scheduled Day | -21 to -1 | 1 | 61 | 183 | 213 | | |
| Scheduling Window | -21 to -1 | Day 1 | ± 21 days | ±28 days | 21 to 49 days after Vacc 3 | | |
| Adverse event monitoring | X | X | X | X | X | | 
Screening to randomization: All AEs, SAEs, and other reportable events that cause the participant to be excluded from the trial or are the result of a protocol-specified intervention are to be reported.
 
Randomization through 14 days following Dose 3: AEs (serious and non-serious) are to be reported from Days 1 through 14 following each vaccination. SAEs, deaths, other reportable events (ie, cancer, overdose, pregnancy, and infant SAEs) are to be reported throughout the duration of an individual's study participation. Exposure during breastfeeding is to be reported from Day 1 through Month 7.
 |
| Review of eVRC data | | | X | X | X | | |
| Reminder contact for urine/saliva self-collection and pregnancy status | | | | | | X | |
| Urine and saliva for CMV | | X | Collected monthly | | | | Self-collected by participant starting at Day 1 (prior to vaccination) and then continue monthly through ~Month 36 or beyond, depending on event accrual |

Vacc = Vaccine; eVRC = Electronic vaccination report card; NAbs = neutralizing antibodies; β-hCG = Human chorionic gonadotropin; IgG = immunoglobulin G; IFN-γ = Interferon gamma; ELISA = Enzyme-linked immunosorbent assay; PBMC = peripheral blood mononuclear cell; DNA = Deoxyribonucleic acid; CMV = Cytomegalovirus; AE = Adverse event; SAE = Serious adverse event

2.2 Schedule of Activities: Follow-up Period Through Approximately Month 36 (Approximate Time Point to Reach Cases Required for Primary Endpoint Assessment)

| Trial period | Follow-up period | | | | | Reminder contacts (monthly) | Notes |
|------------------------------------------------------------------------------------------------------------------------------------------------|-------------------------------|---------------------------------|-------------------------------|---------------------------------|--------------------------------|-----------------------------|-----------------------------------------------------------------------------------------------------------------------------------------------------------------------------------------------------------------------------------------------------------------------------------------------------------------------------------------------|
| Visit number/title | Visit 6 Month 12 Year 1 | Visit 7 Month 18 Year 1.5 | Visit 8 Month 24 Year 2 | Visit 9 Month 30 Year 2.5 | Visit 10 Month 36 Year 3 | | |
| Scheduled Day | 365 | 548 | 731 | 914 | 1096 | | Study closeout activities will be conducted at the participant's closest visit to the end of the study. Close out activities must be completed in the event of early discontinuation. Since the study completion is driven by the primary endpoint (i.e., number of events), the number of visits will depend on the timing of event accrual. |
| Scheduling Window | ± 28 days | ± 28 days | ± 28 days | ± 28 days | ± 90 days | | |
| Reminder contact for urine/saliva self-collection and pregnancy status | | | | | | X | |
| Deaths and SAEs monitoring | X | X | X | X | X | | |
| Participants NOT included in the Detailed Immunogenicity sub-study: Serum for NABs and IgG ELISA antibodies | X | | X | | X | | |
| Detailed Immunogenicity sub-study participants only: Serum for NABs and IgG ELISA antibodies Blood for CMV IFN- γ ELISPOT (PBMCs) | X | | X | | X | | |
| Urine and saliva sample for CMV | collected monthly | | | | | | Self-collected by participant starting at Day 1 (prior to vaccination) and then continue monthly through \approx Month 36 or beyond, depending on event accrual |

SAE = serious adverse event; NABs = neutralizing antibodies; IgG = immunoglobulin G; ELISA = Enzyme-linked immunosorbent assay; ELISPOT = Enzyme-linked immunosorbent spot; PBMC = peripheral blood mononuclear cell; IFN- γ = Interferon gamma

2.3 Schedule of Activities for Congenital Cytomegalovirus Infection Assessment

| Trial period visit number/title | cCMVi visit 1 | Monthly pregnancy contacts | cCMVi visit 2 | Additional cCMVi visit (if necessary) | Reminder contacts (monthly) | cCMVi infant follow-up, yearly contacts for 3 years | Notes |
|----------------------------------------------------------------------------------------------------|--------------------|----------------------------|-----------------------------------------|-----------------------------------------|-----------------------------|-----------------------------------------------------|--------------------------------------------------------------------------------------------------------------------------------------------------------------------------------------------------------------------------|
| Scheduled day | Pregnancy reported | Once per month | Up to 14 days after birth of the infant | Up to 14 days after birth of the infant | | | |
| Scheduling window | - | - | + 7 days | + 7 days | | - | |
| Reminder contact for urine/saliva self-collection and pregnancy status | | | | | X | | |
| Provide instruction on pregnancy and infant follow-up | X | | | | | | |
| Contact from site to assess progress of pregnancy including any suspected congenital CMV infection | | X | | | | | |
| Record anti-CMV treatments received by participants during pregnancy | | X | | | | | |
| Pregnancy/infant outcome assessment | | X | X | X | | | |
| Informed consent for infant urine and saliva sample if live birth | X | | | | | | |
| Infant urine and saliva sample collected for CMV PCR | | | X | X | | | Saliva sample should not be collected within 2 hours of breastfeeding. Two sets of samples (saliva and urine) must be collected at 2 different time points separated by at least 3 hours within 14 (+7) days after birth |
| SAE monitoring and collection for live birth infants | | X | X | X | | X | |
| Yearly follow-up for hearing, vision, and other neurologic outcomes (for infants with cCMVi only) | | | | | | X | |

cCMVi = congenital cytomegalovirus infection; PCR = Polymerase chain reaction

3. Introduction

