 - a. saliva, urine, or other body fluid samples (including the neonatal dried blood spot) obtained within 21 days of birth from an infant born to a study participant;

OR

 - b. amniocentesis fluid obtained from a study participant, or samples from still-birth or products of conception obtained from a study participant.

9.2.1.2.2 cCMVi Case Detection

After a pregnancy is reported to the site, the participant will be asked to come to the site for a study visit (referred to as cCMVi Visit 1).

At this visit, the site staff will explain that the participant's pregnancy will be monitored via monthly contacts from the site until the outcome of the pregnancy is established and recorded. Instructions on when to call the site for any changes in pregnancy status will be provided and an explanation and informed consent/assent regarding follow-up of infant/live birth will also be provided.

For the pregnancy follow-up, medical records of the pregnant study participant will be collected and reviewed by the site personnel to:

- confirm date of conception and expected delivery date
- obtain information on the outcome of the pregnancy
- obtain information that could indicate a suspicion/diagnosis of congenital CMV infection and whether the participant had any related interventions
 - Any anti-CMV treatments received by participants during pregnancy or by infants will be collected for the duration of the trial.
- obtain information that could indicate suspected congenital infection in the infant

All relevant medical records should be placed in the participant's trial file. Infant outcomes will be recorded in the eCRF for all pregnant participants within 24 hours of the delivery or as soon as possible. All pregnancies will be followed to outcome. Refer to Section 9.3.6 for additional requirements for pregnancy follow-up and reporting.

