9.3.6 Pregnancy and Exposure During Breastfeeding

Although pregnancy and infant exposure during breastfeeding are not considered adverse events, any pregnancy or infant exposure during breastfeeding in a participant (spontaneously reported to the investigator or their designee) that occurs during the trial are reportable to the Sponsor. A detailed previous pregnancy history will be collected from all randomized participants who report a pregnancy during the study.

All female participants will undergo pregnancy testing based on serum analysis for β -hCG at screening, and urine sample analysis prior to each vaccination. Participants found to be pregnant at Day 1 are not eligible to participate in the trial and participants are instructed to use effective contraception through Month 7, one month after the treatment phase. All pregnancies that occur during the trial are reportable to the Sponsor.

Participants who inadvertently become pregnant before receiving all 3 doses of study vaccine or placebo, and any participant who becomes pregnant after the treatment phase will remain in the trial for follow-up of pregnancy and infant outcome. Infant SAEs for all infants born to participants who received the study vaccine or placebo or who were breastfed during the treatment phase of the trial must be reported for the duration of the trial.

Infant exposure to vaccination during the treatment phase refers to any participant who is breastfeeding an infant and receives a vaccination; all cases of infant exposure must be reported during the trial. Lactation events do not need to be reported if breastfeeding begins after the treatment phase.

All reported pregnancies in randomized participants must be followed to the completion/termination of the pregnancy. Pregnancy outcomes of spontaneous abortion, missed abortion, benign hydatidiform mole, blighted ovum, fetal death, intrauterine death, miscarriage and stillbirth must be reported as serious events (Important Medical Events). If the pregnancy continues to term, the outcome (health of infant) must also be reported. Refer to Section 9.2.1.2.3 for additional requirements regarding infant outcomes for confirmed cases of cCMVi.

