|----------------------------------------------------------------------------------------------------------------------------------------------------------------------------------------------------------------------------------------------------------------------------------------------------------------------------------------------------------------------------------------------------------------------------------------------------------------------------------------------------------------------------------------------------------------------------------------------------------------------------------------------------------------------------------------------------------------------------------------------------------------------------------------------------------------------------------------|
| 
e. Is a congenital anomaly/birth defect
 
• in offspring of participant taking the product regardless of time to diagnosis |
| 
f. Other important medical events:
 
• Medical or scientific judgment should be exercised in deciding whether SAE reporting is appropriate in other situations such as important medical events that may not be immediately life-threatening or result in death or hospitalization but may jeopardize the participant or may require medical or surgical intervention to prevent one of the other outcomes listed in the above definition. These events should usually be considered serious. 
Examples of such events include invasive or malignant cancers, intensive treatment in an emergency room or at home for allergic bronchospasm, blood dyscrasias or convulsions that do not result in hospitalization, or development of drug dependency or drug abuse.
 |

Additional Events Reported

| |
|--------------------------------------------------------------------------------------------------------------------------------------------------------------------------------------------------------------------------------------------------------------------------------|
| 
Additional Events which require reporting
 |
| 
In addition to the above criteria, adverse events meeting either of the below criteria, although not serious per ICH definition, are reportable to the Sponsor.
 
• Is a cancer;• Is associated with an overdose |

Recording AE and SAE

| |

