Vaccine-type viral shedding will be assessed in V160-vaccinated participants. In addition to the analysis strategy shown in Table 1, point and corresponding 95% CI estimates of incidence of vaccine-type viral shedding (number of participants observed with vaccine-type viral shedding/total person-years of follow-up) will be calculated separately for the V160 3-dose, V160 2-dose, and placebo arms. No treatment group comparisons (V160 vs. placebo or V160

3-dose vs. 2-dose arms) of the percent of participants detected with vaccine-type viral shedding will be conducted.

Summaries of SAEs (throughout the study duration) by system organ class will be provided as incidence rates (number of participants [or infants] observed with a specific SAE/total person-years of follow-up) rather than percentages.

Table 1 Analysis Strategy for Safety Parameters

| Safety Tier | Safety Endpoint | p-value | 95% CI for Comparison of V160 to Placebo | Descriptive Statistics |
|--------------------------------------------------------------------------------------------------------------------------------------------------------------------------------------------------------------------------------------------------------------------------------------------------------------------------------------------------------------------------------|-------------------------------------------------------------------------------|---------|------------------------------------------|------------------------|
| Tier 2 | Solicited injection site AEs ^a | | X | X |
| | Solicited systemic AEs | | X | X |
| | Vaccine-related systemic AEs | | X | X |
| | Any serious AEs (in study participants or infants born to study participants) | | X | X ^b |
| | Vaccine-related serious AEs within Days 1 through 14 after vaccination | | X | X |
| | Discontinuations due to AEs | | X | X |
| | Elevated temperature ^c | | X | X |
| | AEs by SOC observed in ≥7 participants in at least one vaccination group | | X | X |
| Tier 3 | AEs by SOC | | | X |
| | Outcomes of pregnancies | | | X |
| | Vaccine-type viral shedding | | | X [‡] |
| ^a All injection site AEs are considered vaccine-related. ^b Incidence rates (cases/total person-years follow-up) will be provided instead of percentages. ^c Defined as ≥38.0°C [≥100.4°] oral or equivalent AE = Adverse event; CI = Confidence interval; SOC = System organ class; X = indicated summary statistic will be provided. | | | | |

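### After about day 21, SoA 2.3 names infant SAEs only in the yearly cCMVi column, while section 9.3.6 requires them for all infants for the whole trial

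*Combined protocol and SAP*

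**What the plan says.** **The duty.** Protocol section 9.3.6 asks for "Infant SAEs for all infants born to participants who received the study vaccine or placebo or who were breastfed during the treatment phase" to be reported until the trial ends. Section 9.3.1 and the note to the adverse-event row of SoA 2.1 (marked at Visits 1 to 5) also list infant SAEs among the events reportable throughout a woman's participation, whatever the infant's CMV status.

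**The infant schedule.** SoA 2.3 has a row "SAE monitoring and collection for live birth infants" with marks in four columns:

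- the monthly pregnancy contacts; under section 9.2.1.2.2 the pregnancy is "monitored via monthly contacts from the site until the outcome of the pregnancy is established and recorded";
- cCMVi visit 2 and the optional additional visit, each scheduled "Up to 14 days after birth of the infant" with a window of +7 days;
- the column "cCMVi infant follow-up, yearly contacts for 3 years", which section 9.2.1.2.3 and the Figure 1 note give to infants diagnosed with cCMVi.

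The monthly reminder column of SoA 2.3 is blank in this row.

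**The mother's schedule.** SoA 2.2 has a row "Deaths and SAEs monitoring" for every participant at Months 12, 18, 24, 30 and 36. It does not mention infants. The monthly reminder contact has two stated purposes, sample self-collection and pregnancy status.

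**The use.** sSAP Table 1 (protocol Table 5) lists as a Tier 2 endpoint "Any serious AEs (in study participants or infants born to study participants", with a 95% CI for V160 against placebo and incidence per person-year. Protocol Appendix 4 counts as serious a congenital anomaly "in offspring of participant taking the product regardless of time to diagnosis".

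**The concern.** The reporting duty covers all infants for the whole trial, but the schedule that tells sites when to ask does not. Contraception is required through Month 7, so nearly all births fall in the SoA 2.2 period, where infants are no longer named. Once the newborn window closes, the infant of a mother without a cCMVi diagnosis has no contact at which the schedule tells the site to ask about that infant's SAEs. Infants breastfed during dosing are covered by the SoA 2.1 note at visits through Month 7, but no schedule names them after that.

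At stake is the completeness of the infant part of a Tier 2 safety comparison. The documents do not define infant person-years. If they run to trial end, most of the denominator would be time in which nobody was told to ask, and the rates in all arms would be too low. Anomalies diagnosed after the newborn period are within the SAE definition but are not prompted for.

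**Working it through.** The documents give no expected number of births or infant SAEs, so there is no planned figure to reproduce. The check compares the schedules and then sizes the gap under stated assumptions.

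**1. Contacts after a live birth**

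| Contact | Infants reached | Timing | Names infant SAEs? |
|---|---|---|---|
| Monthly pregnancy contact (SoA 2.3) | all | ends when the outcome is recorded | yes |
| cCMVi visit 2 and additional visit | all | 14 + 7 = day 21 at latest | yes |
| Yearly contact (SoA 2.3) | cCMVi infants, per 9.2.1.2.3 and Figure 1 | yearly for 3 years | yes |
| Mother's SAE visits (SoA 2.2) | all, through the mother | days 365, 548, 731, 914, 1096 | no |
| Monthly reminder | all, through the mother | monthly | no |

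**2. Share of the owed time that the infant-specific contacts cover**

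Assumptions: enrolment uniform over 18 months and study end at 36 months (the planned timeline); conceptions at a constant rate after Month 7; 9-month gestation, so births from Month 16; no dropout. The last three are not protocol figures.

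- Follow-up F is uniform on 18 to 36 months, so x = F − 16 is uniform on 2 to 20 months.
- E[x] = 11; Var(x) = 18²/12 = 27; E[x²] = 121 + 27 = 148.
- Mean infant time owed = (E[x²]/2)/E[x] = 74/11 = 6.73 months.
- With c = 21 days = 0.69 month, mean covered time = c − c²/(2 × 11) = 0.67 month.
- Share = 0.67/6.73, about 10%.

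**3. What the mother's visits could add**

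The gaps between SoA 2.2 visits are 183, 183, 183 and 182 days. A conception just after Month 7 (day 213) with an assumed 266-day gestation gives a birth near day 479. Up to four maternal SAE visits then follow (Months 18, 24, 30 and 36). Later births or an earlier study end leave fewer.

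**4. Size of the cCMVi-dependent part**

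Inputs: CMVi incidence of 2% per year on placebo and 0.3% on V160 (VE 85%, section 10.9.1.1); about 40% transmission (section 5.4); an assumed 0.75 year of pregnancy.

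- Placebo: 0.02 × 0.75 × 0.40 = 0.006, or 0.6 cCMVi infants per 100 births. About 99.4% of placebo infants would have no yearly contact.
- V160: 0.003 × 0.75 × 0.40 = 0.0009, or 0.09 per 100.

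| Assumed births per arm | Placebo cCMVi infants | V160 cCMVi infants |
|---|---|---|
| 50 | 0.3 | 0.05 |
| 100 | 0.6 | 0.09 |
| 200 | 1.2 | 0.18 |

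Few of these would reach a yearly contact within the trial. Under the assumptions of step 2, the share of infants who turn 12 months old before Month 36 is E[(x − 12)+]/E[x] = (32/18)/11 = 1.78/11, about 16%. If the first yearly contact comes near the first birthday (assumed), that is 0.6 × 0.16, about 0.1 placebo infant per 100 births.

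**The case against.** The strongest reply is that the duty is already clear. Section 9.3.1 and the SoA 2.1 note make infant SAEs reportable throughout the mother's participation. SoA 2.2 brings every mother to an SAE review about every six months, and section 9.3.2 prefers open-ended questioning by the site. A site reading these together would ask about the child, and case report forms that are not in these documents may prompt for it.

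Much of this stands. A reader might infer from SoA 2.3 that only infants with cCMVi keep any scheduled SAE contact. The documents do not support that, because the mother's visits at Months 12 to 36 are a plausible collection point. If sites use them for infants, the gap reduces to recall over about six months, and the 10% in the working is the share covered by infant-specific contacts only.

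The infant SAE row is also ambiguous. The explicit limit to cCMVi infants sits on the neurologic-outcomes row, not on the SAE row. If the yearly SAE mark was meant for every infant, SoA 2.3 conflicts with section 9.2.1.2.3 and the Figure 1 note, so the passages need reconciling on either reading.

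What the reply does not remove is that a rule on what is reportable does not schedule the question, and from SoA 2.2 onward no contact open to all mothers names infants.

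**Conclusion.** The mismatch between section 9.3.6 and the schedules is real and worth correcting. Its main effect is likely under-collection of infant SAEs after about day 21, for nearly every infant and in all arms. How many SAEs would be lost cannot be computed: the documents give neither births nor infant SAE rates, and site practice at the mother's visits is unknown. The 10% coverage figure rests on the assumed birth timing and counts infant-specific contacts alone.

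Two stronger conclusions are tempting. One is that longer follow-up of cCMVi infants biases the comparison in favour of V160. The direction is conceivable, but the extra contact reaches about one infant per arm or fewer at 50 to 200 assumed births per arm, and fewer still before Month 36, so the effect is negligible. The other is that late-diagnosed anomalies are lost. They remain reportable throughout participation; they are simply not prompted for.

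**What to change.** Reconcile SoA 2.2, SoA 2.3 and section 9.3.6:

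- In SoA 2.2, name infant SAEs in the SAE row at Visits 6 to 10, covering all infants born to the participant or breastfed by her in the treatment phase.
- Add one infant-SAE question to the monthly reminder contact that every participant already receives.
- Use this one schedule regardless of cCMVi status, until the mother's last contact.
- In SoA 2.3, state which infants the yearly SAE mark covers.

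Listing SAEs found only through the yearly cCMVi follow-up separately in the sSAP is optional, given how few infants it concerns.

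No new visit is needed. The cost is one extra question at contacts that already take place and slightly more SAE reports to process.
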